Assessment procedures and measures: Assessments will be conducted at baseline, 3 months post-intervention, 6 months post-intervention, and 9 months post-intervention. Graduated incentives will be used: \$20 for the baseline assessment, \$25 for the 3-month assessment, \$30 for the 6-month assessment, and \$35 for the 9-month assessment. In addition, individuals who complete all 4 assessments will receive a \$50 bonus. Incentives will be prorated contingent on completion of both the objective and subjective indicator outcomes.

Primary outcomes will be economic and behavioral vulnerability to HIV, both of which will be assessed via objective and subjective indicators. Objective indicators for economic vulnerability will include verification of employment, income, housing stability, and savings. Participants will be asked to show a copy or image of a recent pay stub, lease, and bank statement. We will also conduct home visits to verify stable living arrangements and will have information from employers (e.g., hours worked) for participants who are employed through the employment assistance program. Objective indicators for behavioral vulnerability will include verification of HIV testing, verification of linkage to care, verification of enrollment in PrEP (for HIV- participants) and verification of a current prescription for ARVs (for HIV+ participants). Participants will be asked to show a copy or image of a recent physician visit statement or receipt, HIV test result, and/or medication label. Pill counts will be used to assess adherence to biomedical prevention approaches.⁹⁶⁻⁹⁸ Participants will be prompted in advance to bring objective indicators to the assessments but it will also be possible for them to provide information afterwards (e.g., by taking a photo of a bank statement or prescription label and texting it to the project or during a home visit). Subjective indicators for economic vulnerability will include self-reported employment status, hours worked, income, housing status, and savings. Subjective indicators for behavioral vulnerability will include self-reported engagement in transactional sex, number of CSW transactions and partners, unprotected anal/vaginal sex, number and type of sexual partners, and self-reported substance use in conjunction with sexual activity.

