Handling of quantitative data: All participant data stored data collection or data analysis software will be identified by a 3 digit code. Only the PIs and study coordinators will have access to the master file linking participant names with data codes. Computers storing this information will be password protected.

Handling of objective indicators of economic and behavioral vulnerability. As part of the assessment strategy for Aim 3, we will ask participants to show us objective indicators of their economic circumstances and participation in biomedical prevention approaches. This will include verification of employment, income, housing stability, savings account balances, HIV testing, and of linkage to care. We will ask participants to show us a copy of a recent pay stub, their current lease, a bank statement, copies of recent physician visit statements/receipts, HIV test result, or medication labels. Information from these objective indicators will be entered on a data form that records the pertinent details as shown below:

Pay stub: Name of employer, dates worked, hours worked, income

Lease: Home address, beginning and end date of lease

Bank statement: Name of bank, type of account (checking or savings), date of statement, account balances

Physician visits: Name of physician, date of appointment

HIV test result: Date of test, test result

Medication labels: Name of medication, date prescription was filled

On the data form, participants will be identified by their study code. Once the information is recorded, these materials will be returned to the participants. Participants will be reminded in advance to bring objective indicators to the assessment sessions but it will also be possible for them to provide information afterwards (e.g., by taking a photo of a bank statement or prescription label and texting it to the project). If a participant sends us an image of a document, the information will be recorded and then the image will be deleted.

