As noted above, one aspect of the intervention is information/education on biomedical treatments for preventing HIV transmission. These include pre-exposure prophylaxis (PrEP) for HIV-negative participants and anti-retroviral (ARV) regimens for HIV-positive participants. We will encourage HIV testing and PrEP enrollment for our HIV-negative participants and ARV regimens for HIV-positive participants. For both groups, we will provide information and attempt to link them to care with LGBT-friendly service providers. We will also make referrals to LGBT-friendly medical or psychological providers as needed for other needs.

5. * Describe criteria for when the investigator would withdraw an individual participant from the study; such as safety or toxicity concerns, emotional distress, inability to comply with the protocol, etc.:

If a participant is a danger to herself or others we will take appropriate action, including referral for mental health treatment if warranted. Such individuals may be withdrawn from the study.

If a participant is not complying with the ground rules for the intervention (e.g., repeatedly disrespecting or violating the confidentiality of other participants) she could be administratively removed from the study. We consider these events unlikely. These determinations will occur on a case-by-case basis.

6. * Summarize any pre-specified criteria that would trigger the investigator/sponsor/monitoring committee to stop or change the study protocol due to safety concerns:

We do not have pre-specified criteria for stopping or changing the study protocol. However, as this is an intervention development grant and the final intervention utilized will be informed by prior research (e.g., Aim 1 will inform Aims 2 and 3, Aim 2 will inform Aim 3), we may develop pre-specified criteria if we believe it is appropriate to do so. If we develop such criteria, we will inform the IRB and seek approval.

Data and Safety Monitoring

Data and safety monitoring is a system for checking the study's data at regular intervals over the study period to identify and address issues that could affect the safety of research participants. This requirement is in accordance with 45 CFR 46.111.

The purpose of data and safety monitoring plan is to set forth study team procedures for monitoring/addressing:

- Participant safety (physical, psychological, etc.)
- Data validity
- Early stopping (termination) based upon changes in risks and benefits.

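### Linkage to care: the data form does not record what a physician visit was for, so visits unrelated to HIV care or PrEP cannot be excluded

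*Combined protocol and SAP*

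**What the plan says.** Study Procedures, item 7 (Assessment procedures and measures) sets the outcome: "Primary outcomes will be economic and behavioral vulnerability to HIV, both of which will be assessed via objective and subjective indicators". Among the objective behavioral indicators it lists "verification of linkage to care", separately from HIV testing, PrEP enrollment and a current ARV prescription. The evidence requested is described in one sentence: "Participants will be asked to show a copy or image of a recent physician visit statement or receipt, HIV test result, and/or medication label". The visit carries no HIV or PrEP qualifier.

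The fields kept from each document appear under Risks, Discomforts, Potential Harms and Monitoring, item 2 (handling of objective indicators):

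- Visit: "Physician visits: Name of physician, date of appointment"
- Test: "HIV test result: Date of test, test result"
- Label: "Medication labels: Name of medication, date prescription was filled"

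Paper documents go back to the participant once the details are entered. For texted images the rule is: "If a participant sends us an image of a document, the information will be recorded and then the image will be deleted".

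The documents do not define linkage to care, state which visits qualify, list qualifying providers or give a scoring rule.

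**The concern.** The test and label lines carry content that ties them to HIV: a result and a drug name. The visit line does not. A woman seen for HIV care or a PrEP evaluation, with no filled prescription yet, may appear only on the visit line. There she looks the same as a woman seen for something unrelated.

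Because the source is not kept, a scoring rule written at the analysis stage would have nothing to work on. The visit-based part of the indicator would then measure contact with a physician rather than linkage to HIV prevention or treatment. The trial's stated purpose includes estimating effect sizes for later planning, so a diluted estimate would carry forward into the next study.

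**Working it through.** **Plan's own figure.** None is given for linkage to care. The stated power of .88 is for repeated measures ANOVA and does not enter this check.

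**Fields set against indicators.**

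| Evidence | Recorded | Identifies HIV or PrEP content? |
|---|---|---|
| HIV test result | date, result | yes |
| Medication label | drug name, fill date | yes |
| Physician visit | physician, date | no |

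The gap is confined to the last row.

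**Effect of counting unrelated visits.** Let t be the true proportion linked in an arm, and q the share of unlinked women who have some other physician visit.

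Recorded proportion = t + (1 - t)q.

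With the same q in both arms, the recorded difference is (t_I - t_C)(1 - q).

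**Inputs.** The documents give neither t nor q, so both are assumed: t_C = 20%, t_I = 40%, q from 0 to 0.5. The number per arm is 50 × 0.80 = 40, from 50 randomized per arm and the plan's 80% retention. Alpha is not stated and is taken as two-sided 0.05.

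Power for one comparison of two proportions = Φ[(d - 1.96·SE0)/SE1], where d is the recorded difference, SE0 the pooled and SE1 the unpooled standard error. For q = 0:

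- SE0 = √(2 × 0.30 × 0.70 / 40) = 0.1025
- SE1 = √((0.16 + 0.24) / 40) = 0.100
- Power = Φ[(0.20 - 0.2008)/0.100] = 0.50

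| q | Control | Intervention | Difference | Power, 40 per arm |
|---|---|---|---|---|
| 0 | 20% | 40% | 20 points | 0.50 |
| 0.2 | 0.20 + 0.80 × 0.2 = 36% | 0.40 + 0.60 × 0.2 = 52% | 16 points | 0.30 |
| 0.4 | 52% | 64% | 12 points | 0.19 |
| 0.5 | 60% | 70% | 10 points | 0.15 |

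**If q differs by arm.** With equal true linkage t, the recorded difference is (1 - t)(q_I - q_C). Taking t = 30% and q_C = 0.3, a q_I of 0.4 gives 0.70 × 0.1 = 7 false points, and a q_I of 0.6 gives 0.70 × 0.3 = 21. This shows only that the direction is open. No figure in the documents supports any particular q_I.

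**The case against.** Two stronger readings are tempting, and the documents support neither.

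**That any physician visit counts as linkage.** No section says so. The surrounding text points to HIV-specific intent: linkage is listed beside testing, PrEP and ARVs, and Risks item 4 ties linking women to care to PrEP and ARVs. The visit receipt is also not shown to be the only evidence, since the request for documents ends with and/or a medication label, and a PrEP or ARV label could support linkage. This limits the point to the visit-based part of the indicator. It does not supply the missing field.

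**That the form will produce a false effect favoring the intervention.** The argument would be that six early sessions generate more referrals. The relevant sentence is "We will also make referrals to LGBT-friendly medical or psychological providers as needed for other needs". It answers a question about adverse events, applies as needed and names no arm. Controls are due their sessions at six months, so the contrast in contact does not clearly span follow-up. A difference by arm is possible, but nothing shows it.

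Three further objections have some force:

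- The field list sits in a confidentiality section, and the follow-up questionnaire is a separate upload not reproduced here. It may ask the reason for a visit. That answer would be self-report, however, and would not make the objective indicator specific.
- Staff see the document, and the physician's name could be matched to HIV or PrEP providers. No criterion or matching step is written, and a name cannot separate services where one clinician gives several kinds of care.
- The trial is a pilot aimed at estimation, and this is one indicator among many. That lowers the stakes. It does not remove the problem, because effect sizes are what the pilot is meant to deliver.

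**Conclusion.** The point holds in a limited form. As the form is described, visits unrelated to HIV care or PrEP cannot be excluded from the visit-based part of linkage to care, during the trial or afterwards. HIV testing and PrEP or ARV prescription are unaffected.

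If unrelated visits are counted, and equally often in both arms, a true difference shrinks by the factor (1 - q). Under the assumed 20% against 40%, the 20 points become 16 at q = 0.2 and 10 at q = 0.5. These rates are assumptions; the actual size cannot be computed from the documents. The factor itself does not depend on the assumed linkage rates, only on q being equal by arm. The change should be made before data collection, because the lost information cannot be recovered.

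**What to change.** - **Form.** Add two fields to the physician-visit line: purpose (HIV care / PrEP / HIV or STI testing / other) and the source of that purpose (document or self-report).
- **Definition.** State that linkage to care means a visit for HIV care or PrEP within the same look-back window at baseline and at every follow-up, for example the prior 3 months, which matches the assessment spacing. A fixed window is needed because the analysis compares baseline with each follow-up. A rule based on the previous assessment would leave baseline undefined.
- **Scoring.** Count only document-supported purpose as objective verification. Report self-reported purpose separately, and tabulate other visits separately by arm and time point, which would also reveal any difference in q.

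The cost is two tick-box fields on an existing form and a short definition. Some receipts will not show purpose, so fewer visits will qualify as objectively verified. Slightly more sensitive information is recorded, under the certificate of confidentiality already in place.

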(e.g., % engaged in biomedical prevention strategies of ARV use or PrEP). These mixed repeated measures ANOVAs will be conducted between the groups between baseline and each follow-up time point. We hypothesize that the integrated microeconomic intervention group will have reductions in economic and behavioral vulnerability to HIV relative to the wait-list minimal treatment control group. The second primary analysis will involve simple repeated measures ANOVAs for the integrated microeconomic intervention group only. While potential effects of maturation and history weaken our causal conclusions based on this analysis, because of the relatively small sizes of our two groups we feel it will validate our results of the mixed repeated measures ANOVA between the groups. We will use intent-to-treat analyses, using standard assumptions for those in the intervention group lost to follow-up. We will have .88 power to detect a medium effect size ($f^2 = .25$) for repeated measures ANOVA (assuming $r = .5$ for outcomes over time) and .8 power to detect a medium effect size ($f^2 = .15$ or the equivalent of partial $R = .36$) with three predictors for multiple regression. We will also compute effect sizes for use in future power analyses.

During Aim 3, we will also recruit a small number of individuals (10 total across study sites, 5 in Richmond) who report discrimination from religious organizations on the baseline assessment to participate in 60-90 minute qualitative interviews assessing those experiences. These will be digitally recorded and transcribed for qualitative analysis, similar to Aim 1. All protections used in Aim 1 will also be used here. The qualitative interview guide has been uploaded.

8. * The IRB only reviews research procedures, so differentiate which of the study procedures are:

- a. Being performed exclusively for research purposes (i.e. they would not otherwise be done apart from this study).**
- b. Alterations of routine procedures (e.g. the study is altering the timing, frequency, method, location, amount, etc.).**
- c. Being done for other purposes and whose data/results will be used secondarily in the study (e.g. standard medical or psychological tests, routine education practices, quality improvement initiatives, etc.).**

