7. * Indicate if this study will have a Data Safety Monitoring Board (DSMB) or a Data Safety Monitoring Plan (DSMP): [Required for all greater than minimal risk studies]

DSMB

DSMP

No DSMB/DSMP [Note: This response is not applicable for greater than minimal risk studies]

8. * Describe your Data Safety Monitoring Plan for monitoring the study's data to ensure the safety of participants. This plan should include (but is not limited to) the following elements:

1. Who will monitor data
2. What data and/or processes will be reviewed
3. When and how frequently monitoring will occur
4. What report/documentation will be submitted to the IRB at the time of continuing reviews

See the help text for additional guidance.

A Serious Adverse Event (SAE) occurs when any one of the following events happens to a participant enrolled in our research protocol and is brought to the attention of anyone involved with the project: (1) death, (2) life-threatening injury or illness, (3) serious but not life-threatening injury or illness, or (4) participant becomes an immediate risk to the safety of self or others. If project staff become aware than any of these situations have occurred, we will report the

event as described below.

Within 48 hours of becoming aware of an SAE, we will report the event to the Virginia Commonwealth University and University of Missouri-St. Louis Institutional Review Boards as well as the NIH project officer for the study. The report will include a description of the SAE, including date, full chronology of the event based on information available to us, a determination of whether the SAE is related to the study procedures, the steps taken by our staff and/or others to address the SAE, an estimate of the likelihood of the recurrence of the SAE both for the participant and for other study participants, and a discussion of whether the event resulted in new information that indicate that the study procedures should be changed.

In addition to the immediate report of SAEs as described above, we will report any other (i.e., non-serious) adverse events on an annual basis to the Virginia Commonwealth University and University of Missouri-St. Louis Institutional Review Boards as well as the NIH project officer for the study. These steps for reporting SAEs and other adverse events are consistent with our IRB requirements for reporting adverse events.

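### Removal for breaking group ground rules is worded as removal from the study, so randomised outcomes that could still be collected may be lost

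*Combined protocol and SAP*

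**What the plan says.** Risks, Discomforts, Potential Harms and Monitoring, item 5, gives two grounds on which investigators may take a participant out.

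- **Danger to self or others.** The plan says "we will take appropriate action, including referral for mental health treatment if warranted", and then "Such individuals may be withdrawn from the study".
- **Ground rules of the intervention.** A participant who does not comply, for example through repeated disrespect or breaches of other members' confidentiality, "she could be administratively removed from the study".

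Of these removals it adds "We consider these events unlikely" and "These determinations will occur on a case-by-case basis".

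Three other places bear on this.

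- Study Procedures, item 7, Data analysis: "We will use intent-to-treat analyses", with unspecified standard assumptions for intervention participants lost to follow-up.
- Item 8 of the risks section defines a serious adverse event as one that "happens to a participant enrolled in our research protocol and is brought to the attention of anyone involved with the project". It lists as one type "4) participant becomes an immediate risk to the safety of self or others" and sets 48-hour reporting. Withdrawals are monitored by the principal investigators and reported at continuing review.
- The opening of Specific Aim 3 says the trial is mainly meant to assess feasibility and to estimate parameters such as effect sizes and attrition rates.

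**The concern.** Item 5 has a single exit, from the study. It does not say whether a woman who may no longer attend the group is still invited to her follow-up assessments, or how she is analysed.

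For ground-rule removals this is an avoidable loss. The trigger is conduct in a group, while the outcomes are measured on the individual. An investigator's decision after randomisation could therefore end outcome collection for a woman who is reachable and willing. Intent-to-treat needs outcomes on everyone randomised, as far as they can be obtained. A pilot whose product is an attrition estimate also needs to tell women who left from women who were removed.

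For the danger provision the gap is narrower. The plan does not say what happens to outcome assessment and adverse-event reporting after a withdrawal.

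**Working it through.** **1. The plan's own figure.** The concern disputes no figure, but the stated power of .88 gives a scale. Inputs: f = .25, r = .5, m = 4 assessments, N = 100 randomised, two-sided alpha 0.05 (assumed, since none is stated). For the between-group effect, lambda = f²·N·m / (1 + (m−1)·r) = 0.0625·100·4 / 2.5 = 10, which gives power .879 and so matches. The plan prints the effect size as f² = .25. Taken literally that gives .945 or more in every layout tried, so .88 needs f = .25. The match is not unique: 40 people at two time points, tested for the group-by-time effect, gives .869. At the planned 80 completers, lambda = 8 and power is .798.

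**2. Effect of removals on power.** With unequal arms, lambda = (2f)² / [v·(1/n₁ + 1/n₂)], where v = (1 + (m−1)·r)/m = 2.5/4 = 0.625. The documents give no removal rate, so 1 to 5 intervention-arm removals is an assumed range.

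| Starting arm size | 1 removed | 5 removed |
|---|---|---|
| 50 | .876 | .861 |
| 40 | .793 | .769 |

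Power is not the issue.

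**3. Possible shift in an arm's proportion.** If k of n outcomes are unobserved, the proportion in the full arm differs from that in the observed women by (k/n)·(proportion in removed − proportion in observed), so by at most k/n in either direction. For 1 to 5 removals that is 1/50 = 2 points to 5/50 = 10 points, or 1/40 = 2.5 to 5/40 = 12.5 points. These are outer bounds, not estimates.

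**4. Attrition.** Retention of 80% (Study Procedures, item 7, Randomization) implies 50·(1 − 0.80) = 10 losses per arm. If 3 of those 10 were investigator removals (assumed), reported attrition would be 10/50 = 20% while participant dropout was 7/50 = 14%.

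**5. Do the outcomes need the group?** Under Assessment procedures and Measures, self-report is by computer. Documents may be shown, texted later, or seen at a home visit. Contact details are updated monthly. None of this depends on attending a session.

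**6. Balance between arms, ground-rule removals only.** The full intervention has 15 hours of group sessions and the control workshop 3 × 4 = 12 hours (Compensation, item 1). On hours alone the intervention arm has 15/27 = 56% of the exposure, which does not show a marked imbalance. Timing adds to it. The e-mail script (Study Procedures, item 5) puts the control sessions six months later. On that timing a removal during sessions can cost an intervention participant three follow-ups and a control only the 9-month one. With equal removal risk per hour (assumed), the intervention arm bears 15·3 / (15·3 + 12·1) = 45/57 = 79% of lost assessments. This depends on the script's timing. The Assessment procedures paragraph counts months after the intervention and does not say what that means for controls.

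**The case against.** The strongest reply is that item 5 is permissive. It says may and could, decides case by case, calls the events unlikely, and answers a form question that itself asks about withdrawal from the study. The phrase is therefore weak evidence that anyone chose to stop assessments. The Aim 3 consent form and the intervention manual are listed but not available here, and they may describe lesser steps. The investigators also report no adverse events in comparable data from more than 200 transgender women. All of this stands and limits the size of the point. It does not supply the missing statement.

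A reader might go further and infer four things the documents do not support.

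- **That safety follow-up ends for the women at highest risk.** Item 5 provides referral, immediate risk is itself a reportable serious event, and withdrawals are monitored at least monthly. The plan is silent on contact after withdrawal, and silence is not a stop.
- **That a later death would fall outside the serious-event definition.** This needs enrolled to mean still enrolled at the time of the event, which item 8 does not say.
- **That both provisions act on the intervention arm.** Danger to self or others needs no group and can come to light in either arm, for example at an assessment.
- **That the intervention would look better than it is.** Outcomes would be missing, not necessarily excluded. The direction depends on the unspecified standard assumptions, and a conservative one could reverse it.

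**Conclusion.** The point holds in a limited form. Item 5 allows removal from the study for conduct in the group without separating sessions from assessments. It can therefore lose randomised outcomes that remain collectable, which sits poorly with intent-to-treat and mixes two kinds of loss in the attrition estimate.

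Each removal is 2% of a 50-person arm. An imbalance towards the intervention arm at 3 and 6 months is plausible for ground-rule removals only, and only if controls first meet in groups at six months. The number of removals is unknown and probably small. Neither the size nor the direction of any bias can be derived from the documents. For the danger provision, the conclusion is only that item 5, the intent-to-treat statement and the adverse-event rule must be reconciled.

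The change is worth making because it is cheap and missed assessments cannot be recovered later.

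**What to change.** **Ground rules.** In item 5, word this removal as removal from group sessions. State that the participant is still invited to her remaining 3-, 6- and 9-month assessments, unless she withdraws consent or the investigators judge contact unsafe, and that she is analysed as randomised. Report investigator removals by arm, separately from dropout.

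**Danger to self or others.** State whether outcome assessment and 48-hour serious-event reporting continue after withdrawal, so that item 5 agrees with item 8 and with the Data analysis paragraph. Who is withdrawn, and when, stays with the investigators.

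If the consent form or manual already says this, item 5 need only refer to it.

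**Cost.** Wording in one item, a line in the analysis text, and a few assessments arranged away from the group. The assessment incentives and monthly tracking are already planned.
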